8.2.2 Multiplex Opsonophagocytic Assay (MOPA)

The MOPA, developed and published by [name] (Director of the United States World Health Organization pneumococcal serology reference laboratory and National Institutes of Health pneumococcal reference laboratories), is a multiplexed OPA assay

capable of measuring 4 serotypes at a time, against a total of 16 serotypes of pneumococci [Burton, Robert L. and Nahm, Moon H. 2006]. The OPA is an antibody-mediated killing assay that measures the ability of human serum to kill *S. pneumoniae* serotypes with the help of complement and phagocytic effector cells. The ability of the assay to simultaneously test 4 serotypes/run reduces the amount of serum needed for testing. The assay readout is the opsonization index, which is the reciprocal of the highest dilution that gives $\geq 50\%$ bacterial killing, as determined by comparison to assay background controls. Merck Sharp & Dohme Corp. has developed and optimized the MOPA in a high throughput micro-colony platform. The MOPA assay for all 15 V114 serotypes has undergone validation. The validation study evaluated various performance parameters of the assay including precision, relative accuracy/dilutional linearity, and specificity. The validation results were evaluated against pre-specified acceptance criteria for each of the parameters.

8.3 Safety Assessments

Details regarding specific safety procedures/assessments to be performed in this study are provided.

Planned time points for all safety assessments are provided in the SoA.

8.3.1 Physical Examinations

A complete physical examination will be conducted by an investigator or medically qualified designee (consistent with local requirements) as clinically relevant for this patient population before vaccination at Visit 2 (Day 1). A directed physical examination will be conducted by an investigator or medically qualified designee (consistent with local requirements) before vaccination at Visit 3 (Day 30), Visit 4 (Day 60), and Visit 6 (12 months after allo-HSCT).

Investigators should pay special attention to clinical signs related to previous illnesses. A directed physical examination includes obtaining vital signs (heart rate, respiratory rate, blood pressure, body temperature) and a physical examination focused on complaints based on medical history. In the source documents, investigators should document physical exam data and the status of all active medical conditions. Note that temperature is the only vital sign to be collected in the InForm database for this trial.

A complete physical examination includes but is not limited to the assessments of systemic assessment of general appearance, vital signs (heart rate, respiratory rate, blood pressure, body temperature), eyes, throat, mouth, cardiovascular, respiratory, gastrointestinal, skin, neurologic and psychiatric systems, and other organ systems as indicated.

8.3.2 Pregnancy Test

A pregnancy test consistent with local requirements (sensitive to at least 25 IU beta human chorionic gonadotropin [β -hCG]) must be performed before vaccination at Visit 2 (Day 1), Visit 3 (Day 30), Visit 4 (day 60), and Visit 6 (122 months after allo-HSCT) in WOCBP as described in Section 1.3. Pregnancy tests can be repeated as needed based on local

requirements. Urine or serum tests can be used, and results must be negative before vaccination can occur.

8.3.3 Body Temperature Measurement

Prevaccination body temperature will be taken by study staff before vaccination as described in Section 1.3. Participants who have febrile illness (oral temperature $\geq 38.0^{\circ}\text{C}$ [$\geq 100.4^{\circ}\text{F}$] or axillary temperature $\geq 37.4^{\circ}\text{C}$ [$\geq 99.4^{\circ}\text{F}$]) occurring at or within 72 hours of a study vaccination visit must be rescheduled. Oral is the preferred method of obtaining participant's temperature. Axillary (underarm) is an acceptable method for pediatric participants but temperature needs to be confirmed by oral measurement if fever is detected. If an axillary temperature is reported to be $\geq 37.4^{\circ}\text{C}$ ($\geq 99.4^{\circ}\text{F}$), an oral temperature must be taken.

The participant or the participant's legally acceptable representative will be asked to record body temperature using their eVRC during the eVRC-specified postvaccination follow-up period (Section 8.3.4). Adult participants should be instructed to take their post vaccination body temperatures Day 1 through Day 5 following each vaccination. Post vaccination temperatures for pediatric participants <18 years of age should be taken Day 1 through Day 7 following each vaccination by the participant or the participant's legally acceptable representative. For pediatric participants, a temperature measurement must be recorded in the eVRC if fever is suspected during Day 8 through Day 14 postvaccination.

Postvaccination temperature readings should be taken at approximately the same time each day. Temporal or tympanic thermometers to collect temperature for this study is prohibited. All fevers must be reported Day 1 through Day 14, unless the fever is a symptom of another reported AE.

8.3.4 Safety Assessments and Use of the eVRC

All participants will be observed for 30 minutes after each vaccination for any immediate reactions. If any immediate AEs are observed during this period, the time at which the event occurred within this time frame, as well as the event itself, any concomitant medications that were administered, and resolution of the event, must be recorded on the appropriate eCRF.

Adult participants will use the eVRC (Section 8.1.9) to document the following information:

- Oral body temperatures measured Day 1 (day of vaccination) through Day 5 postvaccination;
- Solicited injection-site AEs (redness/erythema, swelling, and tenderness/pain) Day 1 through Day 5 postvaccination;
- Solicited systemic AEs (muscle pain/myalgia, joint pain/arthralgia, headache, and tiredness/fatigue) Day 1 through Day 14 postvaccination;

- Any other injection-site or systemic AEs Day 1 through Day 14 postvaccination; and
- Concomitant medications and nonstudy vaccinations Day 1 to Day 14 postvaccination.

Pediatric participants or the participant's legally acceptable representative will use the eVRC (Section 8.1.9) to document the following information:

Pediatric participants 3 to <18 years of age

- Body temperatures measured Day 1 (day of vaccination) through Day 7 postvaccination; Day 8 through Day 14 postvaccination if fever is suspected
- Solicited injection-site AEs (redness/erythema, swelling, tenderness/pain, and hard lump) Day 1 through Day 14 postvaccination
- Solicited systemic AEs (muscle pain/myalgia, joint pain/arthralgia, headache, tiredness/fatigue, and hives or welts) Day 1 through Day 14 postvaccination
- Any other injection-site or systemic AEs Day 1 through Day 14 postvaccination
- Use of any analgesic or antipyretic on the day of vaccination.
- Concomitant medications and nonstudy vaccinations Day 1 to Day 14 postvaccination.

8.3.5 Clinical Laboratory Assessments

- Refer to Appendix 2 for the list of clinical laboratory tests to be performed and to the SoA for the timing and frequency.
- All protocol-required laboratory assessments, as defined in Appendix 2, must be conducted in accordance with the laboratory manual and the SoA.
- If laboratory values from nonprotocol specified laboratory assessments performed at the institution's local laboratory require a change in study participant management or are considered clinically significant by the investigator (eg, SAE or AE or dose modification), then the results must be recorded in the appropriate CRF (eg, SLAB).
- For any laboratory tests with values considered clinically significantly abnormal during participation in the study or within 30 to 44 days after the last dose of study intervention, every attempt should be made to perform repeat assessments until the values return to normal or baseline or if a new baseline is established as determined by the investigator.

8.4 Adverse Events (AEs), Serious Adverse Events (SAEs), and Other Reportable Safety Events

The definitions of an AE or SAE, as well as the method of recording, evaluating, and assessing causality of AE and SAE and the procedures for completing and transmitting AE, SAE, and other reportable safety event reports can be found in Appendix 3.

Adverse events, SAEs, and other reportable safety events will be reported by the participant or the participant's legally acceptable representative.

The investigator and any designees are responsible for detecting, documenting, and reporting events that meet the definition of an AE or SAE as well as other reportable safety events. Investigators remain responsible for following up AE, SAEs, and other reportable safety events for outcome according to Section 8.4.3.

The investigator, who is a qualified physician, will assess events that meet the definition of an AE or SAE as well as other reportable safety events with respect to seriousness, intensity/toxicity and causality.

8.4.1 Time Period and Frequency for Collecting AE, SAE, and Other Reportable Safety Event Information

All AEs, SAEs, and other reportable safety events that occur after the consent form is signed but before allocation/randomization must be reported by the investigator if they cause the participant to be excluded from the study, or are the result of a protocol-specified intervention, including but not limited to washout or discontinuation of usual therapy, diet, placebo treatment, or a procedure.

All AEs, SAEs, and other reportable safety events must be reported by the investigator from the day of allocation/randomization to the first vaccination and from the day of each vaccination through 14 days postvaccination. SAEs and specific events of interest must also be reported throughout the duration of the individual's participation in the study, regardless of whether or not related to the Sponsor's product.

Additionally, any SAE brought to the attention of an investigator at any time outside of the time period specified in the previous paragraph also must be reported immediately to the Sponsor if the event is either:

- A death that occurs prior to the participant completing the study.

OR

- An SAE that is considered by an investigator who is a qualified physician to be vaccine related.

Investigators are not obligated to actively seek AE or SAE or other reportable safety events in former study participants. However, if the investigator learns of any SAE, including a

death, at any time after a participant has been discharged from the study, and he/she considers the event to be reasonably related to the study intervention or study participation, the investigator must promptly notify the Sponsor.

All initial and follow-up AEs, SAEs, and other reportable safety events will be recorded and reported to the Sponsor or designee within the time frames as indicated in [Table 4](#).

Table 4 Reporting Time Periods and Time Frames for Adverse Events and Other Reportable Safety Events

Type of Event	Reporting Time Period: Consent to Randomization/ Allocation	Reporting Time Period: Randomization/ Allocation through Protocol- Specified Follow- up Period	Reporting Time Period: After the Protocol Specified Follow-up Period	Time frame to Report Event and Follow-up Information to SPONSOR:
Non-Serious Adverse Event (NSAE)	Report if: - due to protocol- specified intervention - causes exclusion - participant is receiving placebo run-in or other run-in treatment	Report all	Not required	Per data entry guidelines
Serious Adverse Event (SAE)	Report if: - due to protocol- specified intervention - causes exclusion - participant is receiving placebo run-in or other run-in treatment	Report all	Report if: - drug/vaccine related. - any death until participant completion of study (Follow ongoing to outcome)	Within 24 hours of learning of event
Pregnancy/Lactation Exposure	Report if: - due to intervention - causes exclusion	Report all	Previously reported – Follow to completion/termination; report outcome	Within 24 hours of learning of event
Event of Clinical Interest	There are no Events of Clinical Interest for this study.			Not applicable
Cancer	Report if: - due to intervention - causes exclusion	Report all	Not required	Within 5 calendar days of learning of event
Overdose	Report if: - receiving placebo run-in or other run-in medication	Report all	Not required	Within 5 calendar days of learning of event

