7 DISCONTINUATION OF STUDY INTERVENTION AND PARTICIPANT WITHDRAWAL

7.1 Discontinuation of Study Intervention

Discontinuation of study intervention does not represent withdrawal from the study.

As certain data on clinical events beyond study intervention discontinuation may be important to the study, they must be collected through the participant's last scheduled follow-up, even if the participant has discontinued study intervention. Therefore, all participants who discontinue study intervention prior to completion of the protocol-specified vaccinations will still continue to participate in the study as specified in Section 1.3 and Section 8.12.3, unless the participant withdraws consent (Section 7.2).

Participants may discontinue study intervention at any time for any reason or be discontinued from the study intervention at the discretion of the investigator should any untoward effect occur. In addition, a participant may be discontinued from study intervention by the investigator or the Sponsor if study intervention is inappropriate, the study plan is violated, or for administrative and/or other safety reasons. Specific details regarding procedures to be performed at study intervention discontinuation are provided in Section 8.1.11.

A participant must be discontinued from study intervention but continue to be monitored in the study for any of the following reasons:

- The participant requests to discontinue study intervention.
- The participant has a medical condition or personal circumstance which, in the opinion of the investigator and/or Sponsor, placed the participant at unnecessary risk from continued administration of study intervention.
- The participant has a confirmed positive urine or serum pregnancy test before any study vaccination visit.

For participants who are discontinued from study intervention but continue to be monitored in the study, see Section 1.3 and Section 8.12.3 for those procedures to be completed at each specified visit.

Discontinuation from study intervention is “permanent.” Once a participant is discontinued, he/she shall not be allowed to restart study intervention.

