9.4.2 Safety Endpoints

A description of safety measures is contained in Sections 8.3 and 8.4. The analysis of safety results is described in Section 9.6.2.

Safety and tolerability will be assessed by clinical review of all relevant parameters separately for adults and pediatric participants, including adverse events and postvaccination temperature measurements following any of the 3 doses of V114 and Prevnar 13TM,

following PNEUMOVAX™23, and following the 4th dose of V114 or Prevnar 13™ (separately).

The safety analysis endpoints for adults (≥18 years of age) include:

- Proportion of participants with solicited injection-site AEs (redness/erythema, swelling, tenderness/pain) from Day 1 through Day 5 postvaccination
- Proportion of participants with solicited systemic AEs (muscle pain/myalgia, joint pain/arthralgia, headache, and tiredness/fatigue) from Day 1 through Day 14 postvaccination
- Proportions of participants with the broad AE categories consisting of any AE, a vaccine-related AE, a SAE, a death, an AE which is both vaccine-related and serious, and discontinuation due to an AE, and the proportion of participants who died
- Proportion of participants with maximum temperature measurements meeting the Brighton Collaboration cut points from Day 1 through Day 5 postvaccination

The safety analysis endpoints for pediatrics 3 to <18 years of age include:

- Proportion of participants with solicited injection-site AEs (redness/erythema, swelling, tenderness/pain, and hard lump) from Day 1 through Day 14 postvaccination
- Proportion of participants with solicited systemic AEs (muscle pain/myalgia, joint pain/arthralgia, headache, tiredness/fatigue, and hives and welts) from Day 1 through Day 14 postvaccination
- Proportions of participants with the broad AE categories consisting of any AE, a vaccine-related AE, a SAE, a death, an AE which is both vaccine-related and serious, and discontinuation due to an AE, and the proportion of participants who died
- Proportion of participants with maximum temperature measurements meeting the Brighton Collaboration cut points from Day 1 through Day 7 postvaccination

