The analysis of safety parameters will be evaluated separately for adult and pediatric participants at 3 separate time points: (1) following administration of any of the 3 doses of V114 and Pevnar 13™ (combined across each of the vaccinations), (2) following administration of PNEUMOVAX™23 (administered 12 months after allo-HSCT), and (3) following administration of a 4th dose of V114 or Pevnar 13™ (administered 12 months after allo-HSCT). Descriptive summaries of AEs following administration of any of the 3 doses of V114 or Pevnar 13™ will include NSAE within 14 days of vaccination and SAEs/special events of interest occurring Day 1 through Month 12 after allo-HSCT (prior to vaccination with PNEUMOVAX™23 or a 4th dose of V114 or Pevnar 13™). Descriptive summaries of AEs following administration of PNEUMOVAX™ will include NSAEs within 14 days of vaccination and SAEs/special events of interest occurring Month 12 after allo-HSCT (Day 1 relative to vaccination with PNEUMOVAX™23) through Month 13 after allo-HSCT (Day 30 relative to vaccination with PNEUMOVAX™23). Descriptive summaries of AEs following administration of a 4th dose of V114 or Pevnar 13™ will include NSAEs within 14 days of vaccination and SAEs/special events of interest occurring Month 12 after allo-HSCT (Day 1 relative to vaccination with a 4th dose of V114 or Pevnar 13™) through Month 13 after allo-HSCT (Day 30 relative to vaccination with a 4th dose of V114 or Pevnar 13™).

The rate of SAEs, vaccine-related SAEs and death that occur throughout the entire study follow-up period will also be summarized per 1000 person-years of follow-up by vaccination group.

In addition, the proportion of participants who have new onset and/or worsening of GVHD as well as relapse and progression of the underlying disease (ie, the disease for which the allo-HSCT was performed [see inclusion criterion 2 in Section 5.1]) during study participation will be summarized descriptively. Limited summaries may also be generated following each of the 3 doses of vaccination of V114 or Pevnar 13™.

Safety analyses will be based on observed data (ie, no imputation of missing data).

Table 6 Analysis Strategy for Safety Parameters

Safety Endpoint	95% CI for Within-Group Comparison	Descriptive Statistics
Injection-site redness/erythema (Days 1 to 5 for adult participants and Day 1 to Day 14 for pediatric participants) [†]	X	X

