Injection-site swelling (Days 1 to 5 for adult participants and Day 1 to Day 14 for pediatric participants) [†]	X	X
Injection-site tenderness/pain (Days 1 to 5 for adult participants and Day 1 to Day 14 for pediatric participants) [†]	X	X
Injection-site hard lump/induration for pediatric participants (Days 1 to 14) [†]	X	X
Muscle pain/myalgia (Days 1 to 14) [†]	X	X
Joint pain/arthralgia (Days 1 to 14) [†]	X	X
Headache (Days 1 to 14) [†]	X	X
Tiredness/fatigue (Days 1 to 14) [†]	X	X
Hives or welts/urticarial for pediatric participants (Days 1 to 14) [†]	X	X
Any AE [‡]	X	X
Any vaccine-related AE [‡]	X	X
Any SAE [‡]	X	X
Any vaccine-related SAE [‡]	X	X
Discontinuation due to AE [‡]	X	X
Death [‡]	X	X
Maximum temperature measurements meeting the Brighton Collaboration cut points (Days 1 to 5 for adult participants and Day 1 to Day 7 for pediatric participants)	X	X
Specific AEs by SOCs and PT		X
[†] Includes solicited events only. [‡] These endpoints are broad adverse event categories. For example, descriptive statistics for the safety endpoint of “Any AE” will provide the number and percentage of participants with at least 1 AE. AE = adverse event; CI = confidence interval; PT = preferred term; SAE = serious adverse event; SOC = System Organ Class; X = results will be provided.		

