9.6.3 Demographic and Baseline Characteristics

The comparability of the vaccination groups for each relevant demographic and baseline characteristic will be assessed by the use of summary tables. No statistical hypothesis tests will be performed on these characteristics. The number and percentage of participants screened and randomized and the primary reasons for screening failure and discontinuation will be displayed. Demographic variables (eg, age, race, and gender), baseline characteristics,

prior and concomitant vaccinations and therapies will be summarized by vaccination group either by descriptive statistics or categorical tables.

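### A non-serious AE that starts more than 14 days after a dose and stops vaccination can fall outside the discontinuation-due-to-AE endpoint, so the within-group proportion may be understated

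*Combined protocol and SAP*

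**What the plan says.** **Endpoint.** For adults and for children, Section 9.4.2 lists among the broad AE categories "an AE which is both vaccine-related and serious, and discontinuation due to an AE". Table 6 in 9.6.2 has a row "Discontinuation due to AE" marked for a within-group 95% CI; 9.6.2 makes that interval an exact binomial one.

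**Reporting.** Section 8.4.1 requires all AEs to be reported "from the day of allocation/randomization to the first vaccination and from the day of each vaccination through 14 days postvaccination". It then adds: "SAEs and specific events of interest must also be reported throughout the duration of the individual's participation in the study". Section 8.4.8 defines the specific events of interest as new or worsening GVHD and relapse or progression of the underlying disease, and lets them be non-serious.

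**Summary.** Section 9.6.2 states that AE summaries after the first three doses "will include NSAE within 14 days of vaccination and SAEs/special events of interest occurring Day 1 through Month 12 after allo-HSCT". The summaries after the Visit 6 dose use the same 14-day limit for non-serious AEs.

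**Stopping.** Under 7.1 a participant may stop study intervention at any time, or "be discontinued from the study intervention at the discretion of the investigator should any untoward effect occur". No time limit relative to a dose is attached.

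**Disposition.** Section 9.6.3 says that "the primary reasons for screening failure and discontinuation will be displayed", again without a 14-day limit.

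**The concern.** The event that defines the endpoint, stopping vaccination, can happen at any time. The AE that explains it is collected only in part of that time, unless it is serious or is GVHD, relapse or progression. The choice to give or withhold a dose arises at the next vaccination visit, which is 29 to 43 days after doses 1 and 2 and months after dose 3.

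Take a non-serious rash that starts on Day 20 after dose 1 and leads the investigator to stop the series. Under 8.4.1 it need not be reported as an AE, and under 9.6.2 it would not be summarised as one. The participant can still appear in the disposition table with an adverse event as the reason, so the two tables could disagree with no stated rule for reconciling them.

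At stake is a direct tolerability measure for a regimen of three doses plus a Visit 6 dose. Missed events can only lower the proportion and its confidence limits.

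**Working it through.** The plan states no expected figure for discontinuation due to an AE, so there is none to reproduce. The check compares the collection window with the time in which a stopping event can arise.

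**Inputs (Section 1.3 and its footnotes)**
- Dose 1: 90 to 180 days after allo-HSCT.
- Doses 2 and 3: Day 30 to Day 44, counting the previous vaccination date as Day 1, so 29 to 43 days apart.
- Visit 6: Day 335 to Day 395 after allo-HSCT.
- Last covered day: Day 14 if the window matches the eVRC diary period (8.3.4), or Day 15 if 14 days after vaccination are counted beyond the vaccination day.

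**Before doses 2 and 3.** Uncovered share = (days before next dose − covered days) / days before next dose.

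| Next dose | Covered through Day 14 | Covered through Day 15 |
|---|---|---|
| Day 30 (29 days) | 15/29 = 52% | 14/29 = 48% |
| Day 44 (43 days) | 29/43 = 67% | 28/43 = 65% |

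The range is 48% to 67%.

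**From dose 3 to Visit 6**
- Shortest: dose 3 at 180 + 43 + 43 = Day 266; 335 − 266 = 69 days. Uncovered: 55/69 = 80% (54/69 = 78% with one more covered day).
- Longest: dose 3 at 90 + 29 + 29 = Day 148; 395 − 148 = 247 days. Uncovered: 233/247 = 94% (232/247 = 94%).

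**Which events the gap affects**

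| AE that leads to stopping vaccination | Reported (8.4.1)? | In the AE summary (9.6.2)? |
|---|---|---|
| Serious, any onset | Yes | Yes, through Month 12 |
| GVHD, relapse or progression, any onset | Yes | Yes, through Month 12 |
| Other non-serious, onset within 14 days of a dose | Yes | Yes, even if it stops a later dose |
| Other non-serious, onset after 14 days | Not required | No |

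Only the last row is lost.

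**Sensitivity to one event (illustration, not an estimate).** Section 9.9.2 gives upper limits for zero SAEs that also hold for any zero count: 1 − 0.025^(1/125) = 2.9% and 1 − 0.025^(1/25) = 13.7%. Both reproduce. Suppose one discontinuation exists and is missed. With 125 adults per group the report would show 0% (upper limit 2.9%) where 1/125 = 0.8% (upper limit 4.4%) is true. With 25 children it would show 0% (13.7%) where 1/25 = 4% (20.4%) is true.

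**The case against.** The strongest reply is that little is left uncaptured. All SAEs, including other important medical events under 10.3.2, and all GVHD, relapse and progression events are collected throughout, and in this population these are plausible reasons to stop. An AE that starts inside the window is followed for outcome (8.4.3) and counts even if a dose is withheld weeks later. Late causes also leave other traces: disposition reasons (9.6.3), documented consultation with the Sponsor on interrupted vaccination (6.4), the number vaccinated at each visit (9.12), and local laboratory values that change management (8.3.5). All of this stands and narrows the gap. None of it puts the event into the discontinuation row.

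A second reply is that Table 4 asks for all non-serious AEs through a protocol-specified follow-up period, under data entry guidelines that are not part of the documents. The Schedule of Activities comment on AE monitoring is also blank in the available text. If either source extends reporting, sites may capture more than 8.4.1 demands. But Table 4 does not define the period, and 9.6.2 would still confine the summary to 14 days.

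Third, a 14-day window for non-serious AEs is a legitimate design choice, and 4.2 says that the safety endpoints and follow-up follow earlier studies. The point is not that the window is wrong in general. This one endpoint depends on events that the window does not bound.

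Three stronger readings are tempting, and the documents do not support them:
- **Share of events missed.** From Day 1 to Visit 6 (335 − 180 = 155 to 395 − 90 = 305 days), three 14-day windows leave 113/155 = 73% to 263/305 = 86% of days uncovered. A reader might take this as the share of events lost. It is a share of time; it would be a share of events only if onset were uniform, which nothing in the documents states. Early clustering after each dose would make the loss smaller.
- **Biased primary safety results.** The listed primary safety endpoints are solicited AEs and vaccine-related SAEs. This gap does not touch them.
- **A bias between groups.** The window is the same in both groups, and the study is estimation only (9.3). The gap does not by itself favour either vaccine.

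**Conclusion.** The point holds in a limited form. For non-serious AEs other than GVHD, relapse or progression, with onset after the 14-day window, neither the reporting rule nor the summary rule lets the event enter the discontinuation-due-to-AE row. The within-group proportion and its 95% CI may therefore be understated; the direction is one-way.

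The size cannot be computed, because no rate of such discontinuations is given. What can be stated is the exposure in time: about 48%–67% of each interval before doses 2 and 3, and about 80%–94% of the interval from dose 3 to Visit 6. Counts for this row may be small, so one missed event could matter, most of all among children.

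This rests on two readings: that the row follows the general AE windows in 9.6.2, since no other window is given for it, and that withholding the Visit 6 dose counts as discontinuation of study intervention, since 7.1 refers to completing the protocol-specified vaccinations and Table 1 includes that dose. After Visit 6 no study vaccine is scheduled, so the gap has no bearing there.

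**What to change.** 1. In 8.4.1, add that any AE, serious or not, that leads to discontinuation of study vaccine is reported whenever it starts between Day 1 and Visit 6. Align Table 4 with this.
2. In 9.6.2 and Table 6, exempt the discontinuation row from the 14-day limit and state its window in a footnote.
3. Reconcile that row with the reasons for discontinuation displayed under 9.6.3, and explain any remaining difference.

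A separate count after Visit 6 is not needed. The cost is a few sentences and a few extra AE forms. The drawback is that this row would have a longer window than the other non-serious AE rows, which the footnote makes plain. The change concerns data capture and tabulation only; it does not alter when vaccination is given or stopped.
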